### **3.4 Patient Registration**

Once clinical eligibility is confirmed, patients must sign an informed consent prior to registration indicating awareness of the investigation nature of the study and its inherent risks in keeping with the policies of the hospital and Federal regulations (Code of Federal Regulations Part 1X, Subpart B, Sections 50.20-50.27).

### **3.5 Removal of Patients From Study**

- Patients may be removed from the study for any of the following reasons:
  - Progression of disease
  - Significant protocol violation
  - Patient non-compliance: defined as any deviation from the protocol without prior agreement of the principal investigator
  - Investigator non-compliance: defined as any significant medical or non-medical deviation from the protocol without agreement of the sponsor
  - Patient's request to withdraw from the study or refusal of further therapy
  - Unacceptable toxicity. A patient may be removed from the study for any complication of treatment that the investigator feels is life threatening.
  - If patient does not meet eligibility criteria

## **4. TREATMENT PLAN**

No investigational or commercial agents or therapies other than those described below may be administered with the intent to treat the patient's malignancy. Interferon alpha-2b and 5-FU/Capecitabine are available commercially and a commercial supply will be used for this study.

### **4.1 Capecitabine Administration**

Drug administration will be on an outpatient basis. Capecitabine will be administered at an initial dose of 800 mg/m^2 by mouth twice daily on days 1-14 of a 21 day cycle with days 15-21 off. This cycle will be repeated every 21 days during the study for a maximum of 9 cycles as tolerated. Administration via feeding tube in patients unable to swallow is permitted. For severe side effects, dose reductions are listed in Table 5. Reported adverse events and potential risks are described in Section 6.

Capecitabine tablets should be swallowed with water within 30 min after a meal. The calculated dose by body surface area (BSA) will be rounded down to allow as close to as total daily dose of 1600 mg/m^2 divided as closely as possible into AM and PM doses of 800 mg/m^2 using a combination of 150 mg and 500 mg tablets. There will be no modification of BSA calculation based on idealized body weight or other corrective factor.

**4.1.1 Storage:** Capecitabine tablets should be kept a room temperature

**4.1.2 Pill Diary:** The patient will be requested to maintain a medication diary for review at the end of each cycle of treatment and reconciled with a pill count.

If the patient is clinically stable after 3 cycles, then a diary review and pill counts may be discontinued.

#### **4.1.3 Supportive Care Guidelines**

Capecitabine has a low emetogenic potential. Routine anti-emetics are not recommended but may be used at the treating physician's discretion. Standard use of anti-diarrheal agents is permitted.

#### **4.2 5-FU Administration**

If patients are not able to acquire oral capecitabine, then we will start patients on infusional 5-FU which can be delivered via standard of care. Patients will need to have a port placed for continuous infusion treatments. 5-FU pumps will be activated in the infusion center at Moffitt Cancer Center with a starting dose of 800 mg/m^2 days 1-4, with pump removal on day 5 at the infusion center. 5-FU pumps will be attached every 21 days (1 cycle) for a maximum of 9 cycles. For severe side effects, dose reductions are listed in Table 5. Reported adverse events and potential risks are described in Section 6.

##### **4.2.1 Storage**

Drug stored in pharmacy per manufacturer's instructions.

##### **4.2.2 Supportive Care Guidelines**

5-FU has a low-medium emetogenic potential. Routine anti-emetics may be used at the treating physician's discretion. Standard use of anti-diarrheal agents is permitted.

#### **4.3 Interferon Administration**

Drug administration will occur on an outpatient basis at the infusion center at Moffitt Cancer Center. Dose will be weight-based. Starting treatment doses of 3 mcg/kg will be given SC injection in the thigh, abdominal wall, or upper arm every week for a total of 27 weeks as tolerated. Patients will be premedicated with 650 mg of acetaminophen or 400 mg of ibuprofen as tolerated. For severe side effects, dose reductions are allowed as discussed in Section 5. Reported adverse events and potential risks are described in Section 6.

4.3.1 Storage: Drug stored in pharmacy per manufacturer's instructions.

##### **4.3.2 Supportive Care Guidelines**

Anti-pyretics such as ibuprofen and acetaminophen can be used as directed to manage low grade fevers and muscle/joint pains. Anti-nausea and anti-diarrheal agents can be used at the treating physician's discretion.

#### **4.4 Duration of Therapy**

In the absence of treatment delays due to adverse event(s), treatment may continue for 9 cycles or until one of the following criteria applies:

- Disease progression,
- Concurrent illness that prevents further administration of treatment,
- Unacceptable adverse event(s),
- Patient decides to withdraw from the study, or

X General or specific changes in the patient's condition render the patient unacceptable for further treatment in the judgment of the investigator.

#### **4.5 Duration of follow up**

Patients will be followed for up to one year after removal from study or until death. Patients removed from the study for unacceptable adverse event(s) will be followed until resolution or stabilization of the adverse event.

### **5. DOSING DELAYS/DOSE MODIFICATIONS**

#### **5.1 5-FU/Capecitabine**

A dose reduction will be instituted upon any grade 3 or 4 toxicity that is attributable to 5-FU/capecitabine. For all grade 3 or 4 toxicities related to 5-FU/capecitabine, the study treatment will be withheld for up to 3 weeks until the toxicity has resolved to CTCAE grade 1 or better (or back to baseline), and then treatment may be restarted. Dose reduction/re-challenge for each toxicity criterion will be managed as discussed in the sections that follow. Patients will be withdrawn from the study if toxicity does not resolve to  $\leq$  CTCAE grade 1 (or to baseline) within 3 weeks.

#### **Myelosuppression**

On Day 1 of each cycle, if the neutrophil count is  $< 1000/\text{mm}^3$ , or the platelet count is  $< 75,000/\text{mm}^3$ , then treatment with 5-FU/capecitabine will be held until the neutrophil count is  $\geq 1000/\text{mm}^3$ , and platelet count is  $\geq 75,000/\text{mm}^3$ . Once restarted, 5-FU/Capecitabine will be dose reduced per Table 1. If treatment is required to be held for  $\geq 3$  weeks, then study treatment will be discontinued.

#### **GI Toxicity**

Nausea, vomiting, or both may be controlled with antiemetic therapy. Diarrhea should be treated with standard medications to avoid dose modification or interruption, if possible. Electrolyte supplementation with regular laboratory monitoring should be used, when appropriate, to maintain electrolytes within normal limits.

Dose modifications for diarrhea will be as follows:

If  $\geq$  grade 3 diarrhea refractory to oral anti-diarrheal medication occurs, treatment will be held until the toxicity is  $<$  grade 2, then the 5-FU/capecitabine dosage will be reduced according to Table 2 shown below. If treatment must be withheld for more than 3 weeks for resolution of diarrhea, the patient will not restart treatment and the patient will be withdrawn from the study.

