#### **Mucositis or Hand/Foot Syndrome (HFS)**

If  $\geq$  grade 3 mucositis or HFS occurs, 5-FU/capecitabine will be interrupted for a minimum of 1 week. If the toxicity has not improved to  $<$  grade 2, the treatments will be held for up to 2 additional weeks. Once restarted, the dose of capecitabine will be reduced according to Table 2. If treatment is required to be held for  $\geq 3$  weeks, then study treatment will be discontinued.

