#### **Other toxicities**

If  $\geq$  grade 3 toxicities directly attributable to 5-FU/capecitabine other than those discussed above occur (except fatigue, alopecia, or nausea/emesis in the absence of anti-emetics), therapy will be discontinued until the toxicity is  $<$  grade 2. If there is no evidence of tumor

progression, therapy may resume with a dose reduction according to Table 1. If treatment is required to be held for  $\geq$  3 weeks, then study treatment will be discontinued.

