**TABLE 1: Capecitabine dose levels**

Dose Level	5-FU/Capecitabine Dose
-2	400 mg/m  per 21 day cycle
-1	600 mg/m 
0 ( starting dose)	800 mg/m 

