**TABLE 2: IFN alpha-2b dose levels**

Dose Level	IFN alpha-2b
-2	1 mcg/kg SQ q week per 21 day cycle
-1	2 mcg/kg SQ q week per 21 day cycle
0 ( starting dose)	3 mcg/kg SQ q week per 21 day cycle

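### Two 5-FU/capecitabine dose-reduction rules point to the interferon dose table, sections 4.1 and 4.2 cite a Table 5 that does not appear, and the mucositis/hand-foot rule gives two answers at a hold of exactly 3 weeks

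*Combined protocol and SAP*

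**What the plan says.** Section 5.1 opens with a general rule for grade 3 or 4 toxicity attributed to 5-FU/capecitabine. Treatment is "withheld for up to 3 weeks until the toxicity has resolved to CTCAE grade 1 or better (or back to baseline") and may then restart; the patient is withdrawn if recovery does not come within that time. The opening paragraph leaves reduction and re-challenge for each toxicity to the rules after it.

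Four specific rules follow:

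- Myelosuppression: "Once restarted, 5-FU/Capecitabine will be dose reduced per Table 1".
- Diarrhea, under GI Toxicity: "then the 5-FU/capecitabine dosage will be reduced according to Table 2 shown below".
- Mucositis or hand-foot syndrome: "Once restarted, the dose of capecitabine will be reduced according to Table 2".
- Other toxicities: "therapy may resume with a dose reduction according to Table 1".

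Table 1, at the end of section 5.1, has a column headed "5-FU/Capecitabine Dose" with levels of 800, 600 and 400 mg/m². Table 2, at the end of section 5.2, is "TABLE 2: IFN alpha-2b dose levels" and lists 3, 2 and 1 mcg/kg weekly.

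Sections 4.1 (capecitabine) and 4.2 (5-FU) contain the same sentence: "For severe side effects, dose reductions are listed in Table 5". The parallel sentence in section 4.3 (interferon) refers to Section 5.

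The mucositis/hand-foot rule sets a minimum interruption of 1 week, allows up to 2 further weeks if the toxicity is not yet below grade 2, and discontinues study treatment if the hold has to last 3 weeks or more.

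**The concern.** These are working dosing rules that staff consult when a patient has a severe toxicity. Section 6.1 lists diarrhea, stomatitis and hand-foot syndrome among the expected toxicities of 5-FU/capecitabine, so the two rules that cite the wrong table are likely to be used. Read literally, they send a fluoropyrimidine reduction to a table that has no fluoropyrimidine dose.

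The hold limit raises a separate question: who stays on treatment. If a rule both allows and forbids restart after the same hold, two patients with the same course can be handled differently. Section 3.5 makes deviation from the protocol without prior agreement a possible ground for removal, and section 10.2.2 has the monitoring committee review deviations. At that boundary the rule could not be audited.

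**Working it through.** No sample-size, power or error-rate figure bears on this point, so the check is a side-by-side reading.

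**Table references for reducing 5-FU/capecitabine**

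| Place | Table cited | What is there | Correct? |
|---|---|---|---|
| 4.1 Capecitabine Administration | Table 5 | not in the text | no |
| 4.2 5-FU Administration | Table 5 | not in the text | no |
| 5.1 Myelosuppression | Table 1 | 5-FU/capecitabine levels | yes |
| 5.1 GI Toxicity (diarrhea) | Table 2 | interferon levels only | no |
| 5.1 Mucositis or hand-foot syndrome | Table 2 | interferon levels only | no |
| 5.1 Other toxicities | Table 1 | 5-FU/capecitabine levels | yes |

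Count: 2 correct + 4 wrong = 6. Within section 5.1 alone, 2 of the 4 specific rules are wrong. For comparison, the five interferon rules in section 5.2 (fatigue, arthralgia/myalgia, weight loss, depression, GI toxicity) all cite Table 2, which is right: 5 of 5. The slip is confined to 5-FU/capecitabine.

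**The mucositis/hand-foot hold**

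- Longest hold allowed: 1 week + up to 2 weeks = 3 weeks = 21 days.
- Hold that ends treatment: 3 weeks or more.
- Overlap: a hold of exactly 3 weeks meets both conditions. Shorter holds lead to restart and longer ones to discontinuation, without ambiguity.

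A hold of 3 weeks equals one 21-day cycle. The study calendar in section 8 schedules examination, blood count and chemistry at weeks 1, 4 and 7. A patient held on Day 1 of a cycle therefore has the next scheduled assessment 3 weeks later. Earlier unscheduled checks are possible, and these toxicities can begin mid-cycle. The documents give no frequency for holds of this length, so none is estimated.

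**Limits across section 5.1 at exactly 3 weeks**

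- General rule: restart allowed.
- Diarrhea: restart allowed, because discontinuation needs more than 3 weeks.
- Myelosuppression: discontinue.
- Other toxicities: discontinue.
- Mucositis/hand-foot: both, as shown above.

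Because the general rule passes re-challenge to the specific rules, the different limits for diarrhea, myelosuppression and other toxicities can stand side by side. Only the mucositis/hand-foot rule is inconsistent within itself.

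**The case against.** The strongest reply is that nobody would be misled. Both faulty rules name the drug, Table 2 is in mcg/kg, and the next table below those rules is Table 1. This stands: a reader might infer a route to a wrong dose, but the documents do not support that, because Table 2 offers no figure that could be taken for a capecitabine dose. What remains is that two safety rules do not contain the instruction they claim to give.

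A reader might also infer that section 5.1 as a whole conflicts at 3 weeks. It need not. The opening paragraph defers to the specific rules, different toxicities may have different limits, and a protocol need not justify each one.

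The mucositis/hand-foot rule can be defended in a similar way: the 2 extra weeks are a ceiling on waiting, and the last sentence applies to a patient who still needs a hold when that ceiling is reached. That is a possible reading, but the text does not state it. It speaks only of the length of the hold, so a patient who recovers on the final permitted day still meets the discontinuation condition.

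Could a redaction hide Table 5? Probably not. The visible redacted block follows section 11.4, where the table of contents places the correlative studies. More likely Table 5 is a slip, either for Table 1 or for Section 5, which section 4.3 cites in the same context.

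Finally, a reader might see a gap in the interferon fatigue rule, whose printed trigger is above grade 3. That rests on a single symbol in text extracted from a PDF, and the general rule in section 5.2 already requires a hold and reduction for any grade 3 or 4 interferon toxicity. It is not part of this point.

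**Conclusion.** The point holds in a limited form. Four of the six table references for reducing 5-FU/capecitabine are wrong: two name the interferon table and two name a table that is not in the text. One rule, for mucositis or hand-foot syndrome, gives two answers at a hold of exactly 3 weeks and at no other length.

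This rests on two assumptions: that the text as supplied contains all the numbered dose tables, and that the specific rules in section 5.1 govern over the general one, as its opening paragraph suggests. There is no effect on type I error, power or the response denominator. These are drafting errors in operative safety rules and should be corrected because they decide dosing and discontinuation and cost almost nothing to put right.

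**What to change.** 1. In section 5.1, change Table 2 to Table 1 in the diarrhea rule and in the mucositis/hand-foot rule.
2. In sections 4.1 and 4.2, replace Table 5 with Section 5 (Table 1). This matches section 4.3 and leads the reader to the hold and restart rules as well as the dose levels.
3. In the mucositis/hand-foot rule, discontinue only when the hold exceeds 3 weeks. This agrees with the rule's own 1 + 2 weeks and with the general rule in section 5.1.
4. Ask the investigator to confirm that the limits for myelosuppression, diarrhea and other toxicities differ on purpose. No edit is needed if they do.

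The cost is four corrected references, one changed threshold and one confirmation. The third change is a small clinical decision as well as a wording change: patients who recover at exactly 3 weeks may restart, at a reduced dose. Sample size and analysis are unchanged.

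### Section 5.1 sends the 5-FU/capecitabine reduction for diarrhea, mucositis and hand-foot syndrome to Table 2, which holds only interferon doses; the right table is Table 1

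*Combined protocol and SAP*

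**What the plan says.** Section 5.1 of the protocol governs dose changes for 5-FU/capecitabine. Its general rule makes a reduction mandatory: "A dose reduction will be instituted upon any grade 3 or 4 toxicity that is attributable to 5-FU/capecitabine". It leaves the details to the toxicity paragraphs that follow. Four of these name a table:

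- Myelosuppression: "5-FU/Capecitabine will be dose reduced per Table 1".
- GI toxicity, on diarrhea of grade 3 or worse that does not respond to oral medication: "the 5-FU/capecitabine dosage will be reduced according to Table 2 shown below".
- Mucositis or hand-foot syndrome of grade 3 or worse: "Once restarted, the dose of capecitabine will be reduced according to Table 2".
- Other toxicities: "therapy may resume with a dose reduction according to Table 1".

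Table 1 closes Section 5.1. Its title mentions capecitabine only, but its dose column is headed "5-FU/Capecitabine Dose", and its levels are 800, 600 and 400 mg/m². The second table closes Section 5.2 and is titled "TABLE 2: IFN alpha-2b dose levels"; its levels are 3, 2 and 1 mcg/kg weekly by subcutaneous injection.

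**The concern.** Two paragraphs order a reduction of one drug and cite the ladder of the other. The reduction is compulsory, yet the cited table offers no step in mg/m². The person writing the order has to notice the mismatch and infer which table was meant.

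These are not remote events. Section 6.1 lists diarrhea, stomatitis and hand-foot syndrome among the expected toxicities of 5-FU/capecitabine. Diarrhea is also on the interferon list in Section 6.2, and the interferon GI paragraph in Section 5.2 properly cites Table 2. For severe diarrhea, then, the rules for both drugs name the interferon table. At stake are the clarity of a safety instruction and the consistency with which patients are stepped down.

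**Working it through.** The check is a cross-reference audit. The plan states no figure to reproduce here, and no power or error-rate calculation is involved.

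**Step 1. Table cited against drug to be reduced.**

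| Section and paragraph | Drug to be reduced | Table cited | Does that table list the drug? |
|---|---|---|---|
| 5.1 Myelosuppression | 5-FU/capecitabine | 1 | Yes |
| 5.1 GI toxicity (diarrhea) | 5-FU/capecitabine | 2 | No |
| 5.1 Mucositis or HFS | capecitabine (5-FU not named) | 2 | No |
| 5.1 Other toxicities | 5-FU/capecitabine | 1 | Yes |
| 5.2 Fatigue, arthralgia/myalgia, weight loss, depression, GI | interferon | 2 | Yes |

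In Section 5.1, 2 of 4 citations are wrong, covering three named toxicities (diarrhea, mucositis, hand-foot syndrome). The Section 5.2 citations are right.

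**Step 2. Could Table 2 be used anyway?** All three of its rows are in mcg/kg of interferon. Rows giving a 5-FU or capecitabine dose: 0 of 3.

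**Step 3. What the correct table gives.** From the 800 mg/m² starting level:

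- Level -1: 600/800 - 1 = -25%.
- Level -2: 400/800 - 1 = -50%.

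**Step 4. Is there an artefact or another source?** Both tables are present with titles and rows intact. The wrong citations stand in current operative text, and no redaction is marked in Section 5. Sections 4.1 and 4.2 do not resolve the matter: they refer to a Table 5 for dose reductions, and the supplied document has none.

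**Step 5. Two adjoining wording points.**

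- The mucositis/HFS paragraph interrupts both fluoropyrimidines but names only capecitabine when it orders the reduction. Read literally, it gives no step for a patient on infusional 5-FU.
- Section 4.2 gives 5-FU as 800 mg/m² over days 1-4 without a time unit. Per day, the cycle total is 4 × 800 = 3,200 mg/m²; as a total over the infusion it is 800 mg/m². The readings differ by 3,200/800 = 4. Per day is probably meant, but the text does not say so.

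**The case against.** The strongest reply is that nobody would be misled. The protocol has one fluoropyrimidine ladder. It is the first table after the two paragraphs, it is in the right units, and two neighbouring paragraphs cite it for the same drug. The diarrhea paragraph names the drug to be reduced, and a weekly mcg/kg injection schedule cannot be applied to oral capecitabine or a 5-FU pump. The general rule still requires the hold and the reduction whatever table number is printed. This largely stands, and it limits the weight of the point. It does not remove the error: a rule for grade 3 or worse toxicity should be executable from the table it cites.

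Three stronger readings are tempting and are not supported.

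- A reader might infer that staff would reduce interferon instead of the fluoropyrimidine. Both paragraphs name the fluoropyrimidine, and nothing in the documents shows a concrete route to that mistake. Naming the same table in both diarrhea rules adds some room for confusion, no more.
- A reader might infer that Table 5 in Sections 4.1 and 4.2 must mean Table 1. The parallel sentence for interferon in Section 4.3 refers to Section 5, so a slip for Section 5 is equally plausible. Only the sponsor can say.
- A reader might infer from the bottom row of Table 1, "400 mg/m 2 per 21 day cycle", that dosing schedules are missing. Section 4.1 gives capecitabine twice daily on days 1-14, and Section 4.2 gives the 5-FU infusion days. Nothing indicates that a reduction changes these schedules. Repeating them in Table 1 would be a matter of preference.

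The naming of capecitabine alone in the mucositis/HFS paragraph may also be shorthand, since the title of Table 1 does the same. It is still worth correcting while the sentence is open.

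**Conclusion.** The inconsistency is real: two of the four toxicity paragraphs in Section 5.1 cite a table that contains no dose of the drug they order reduced. It should be corrected because it sits in an operative dosing rule for toxicities that the protocol expects. Its weight is modest because the intended table is evident.

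The effect is confined to dosing safety and consistency between patients. A reader might infer that the trial's conclusions are at risk. The documents give no ground for that: the response criteria, the two-stage boundaries (at least 2 of 16, then at least 5 of 25), the planned enrolment of 30 and the survival analyses do not depend on the table number.

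The conclusion rests on the text of Sections 5.1 and 5.2 and the two tables. The one inference is that Table 1 was meant, supported by its column heading, its units, its position and the two correct citations. The Table 5 reference and the 5-FU time unit are related questions for the sponsor and do not add to the weight of this point.

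**What to change.** In Section 5.1, change the table number from 2 to 1 in the diarrhea paragraph and in the mucositis/HFS paragraph. In the latter, order the reduction for 5-FU/capecitabine rather than capecitabine alone.

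In the same amendment, ask the sponsor to:

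- correct the Table 5 reference in Sections 4.1 and 4.2, to Table 1 or to Section 5 as intended;
- confirm that the 800 mg/m² of 5-FU in Section 4.2 is per day, and write the unit in.

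The cost is very low: four cross-references, one drug name and one unit. Section 10.2.1 requires IRB approval before any protocol change takes effect, so these edits can reasonably go into the next amendment. Sample size, decision rule and analysis stay as they are.
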